### **10.2.5 Clinical Laboratory Evaluations**

A change in the value of a safety laboratory investigation can represent an AE if the change is clinically relevant in the opinion of the Investigator or if, during treatment with the study treatment, a shift of a parameter is observed from a normal value to a pathological value, or a further worsening of an already pathological value.

If, at the end of the treatment phase, there are pathological laboratory values which were not present at baseline, further clinical or laboratory investigations will be performed until the values return to within reference range or until a plausible explanation (e.g., concomitant disease) is found for the pathological laboratory values.

If the Investigator considers such an AE as serious it must be reported as an SAE.

### **10.2.6 Abuse, Misuse, Overdose and Medication Error**

All AEs of special interest such as study treatment abuse, misuse, overdose, and medication error have to be documented in the subject's eCRF and source documentation. If any occurrence of abuse, misuse, overdose, or medication errors leads to any event that fulfils any seriousness criteria, the event has to be reported as an SAE.

## **10.3 Reporting Procedure for AEs, SAEs, and Pregnancy**

### **10.3.1 Adverse Events**

All AEs either observed by the Investigator or one of his/her medical collaborators, or reported by the subject spontaneously, or in response to a direct question, will be noted in the AE section of the subject's eCRF and source documentation. This applies to all AEs regardless of presumed relationship to the study treatment. Adverse events leading to discontinuation of study treatment must be collected.

If any AE is reported, the date of onset, relationship to disease under study, relationship to study treatment, any action taken, date of resolution (or the fact that it is still continuing or has become chronic), outcome, and whether the AE is serious or not, will be recorded. Use of colloquialisms and abbreviations should be avoided. Only 1 AE term should be recorded in the event field on the AE eCRF. Where possible, the Investigator should report a diagnosis rather than signs and symptoms or abnormal laboratory values. However, if a constellation of signs and/or symptoms cannot be medically characterized as a single diagnosis or syndrome at the

time of reporting, each individual event should be recorded on the AE eCRF. If a diagnosis is subsequently established, all previously reported AEs based on signs and symptoms should be nullified by the Investigator and replaced by one AE report based on the single diagnosis, with a starting date that corresponds to the starting date of the first symptom of the eventual diagnosis.

The AE reporting period begins at the time the ICF is signed by the subject. The AE reporting period ends at the study follow-up visit (Visit 24). Adverse events persisting at the time of study completion will be followed by the Investigator through contact with the subject until resolution or stabilization has occurred (or the subject is lost to follow-up and cannot be contacted) and recorded in the source documents. If the subject reports an AE, it is the Investigator's responsibility to acquire sufficient information in order to assess causality. This may require additional laboratory testing, physical examinations, telephone contacts, etc. In circumstances where the Investigator is unable to make contact with the subject, the Investigator must provide a written statement to Aurinia confirming that the subject is lost to follow-up.

In order to avoid bias in eliciting AEs, subjects should be asked a non-leading question, such as "How are you feeling?" It is also important to question the subject in a non-leading way about changes in their health or concomitant medication usage since their last visit. This information should be collected prior to completion of assessments at all study visits. In addition, any symptoms/conditions reported during assessments and deemed to be clinically significant by the Investigator will be considered AEs.

### **10.3.2 Serious Adverse Events**

All SAEs occurring after the signing of the ICF will be reported to [REDACTED] within 24 hours of the Investigator, designee, or site staff's knowledge of the event regardless of relationship to study treatment or relationship to disease under study. All SAEs are to be reported on the eCRFs.

In the event that the site experiences a temporary disruption of the EDC system a back-up paper SAE Reporting Form will be available for site staff to complete.

- Site staff will complete the paper SAE report form and e-mail it within 24 hours to the following address: [REDACTED]
- Only in cases where the email system is unavailable, site staff will send the SAE by fax to: [REDACTED] (US) and [REDACTED] (Outside US).

If notification is made via email or fax, site staff must enter the SAE information into the EDC system as soon as the system becomes available.

All SAEs, regardless of causality, will be reported from the time the ICF is signed until 30 days following the last study visit or 30 days after last study treatment administration in subjects who withdraw or discontinue prior to study completion. No formal study visit is required but Investigators must report any SAEs that occur during this 30 day period on the eCRF. If the Investigator has not seen the subject at a clinic visit at the end of the reporting period, the Investigator must make reasonable efforts to contact the subject to inquire about SAEs.

All recorded SAEs, regardless of relationship to disease under study or relationship to study treatment, will be followed up until resolution, stabilization, or the subject is lost to follow-up and cannot be contacted. In circumstances where the Investigator is unable to make contact with the subject, the Investigator must provide a written statement to Aurinia confirming that the subject is lost to follow-up.

Any SAE considered to have a causal relationship (i.e., “related”) to the study treatment and discovered by the Investigator at any time after the study will be reported. A rationale for the assessment of a causal relationship must be provided by the Investigator. The Investigator will also be required to assess the relationship to disease under study for each SAE as related or not related. An SAE will not be able to be assessed as related to both disease under study and related to study treatment. Any safety information that is obtained after the Follow-up Visit (Visit 24) will be documented in the safety database only.

A death occurring during the study or which comes to the attention of the Investigator within 30 days after the last study visit (including the Follow-up Visit) or until 30 days after the last study treatment administration, whichever is longer, whether considered treatment-related or not, must be reported to Aurinia-. If the subject died, the SAE report should include the cause of death as the event term and whether or not the death was related to study treatment, as well as the autopsy findings, if available. Preliminary reports will be followed by detailed descriptions which will include copies of hospital case reports, autopsy reports/certificates and other documents when requested and applicable.

Additional follow-up information must be reported in the eCRF within 24 hours of awareness following Investigator (or site) awareness of the information. The Investigator should not delay reporting an SAE in order to obtain additional information. Additional information, when available, should be reported to [REDACTED] by the reporting procedures described above.

The Investigator is encouraged to discuss with the study Medical Monitor when the issue of seriousness is unclear or questionable.

An Investigator who receives an Investigator safety report describing an SAE or other specific safety information (e.g., summary or listing of SAE) from the sponsor will file it along with the IB and will notify the IRB/IEC, if appropriate according to local requirements.

The sponsor or its representative will be responsible for determining and, in turn, reporting SAEs to regulatory authorities according to the applicable regulatory requirements.

### **10.3.3 Pregnancy**

Pregnancy occurring in a female subject or in the partner of a male subject should be reported to [REDACTED] within 24 hours of becoming aware of the event using the pregnancy eCRF. The Investigator should counsel the subject, and in the case of a male subject, the subject's partner, discuss the risks of continuing with the pregnancy and the possible effects on the fetus. A female subject must immediately inform the Investigator if she becomes pregnant during the study. Monitoring of the pregnancy in a female subject should continue until conclusion of the pregnancy. In case of a pregnancy in the partner of a male subject, the Investigator should obtain informed consent of the pregnant partner prior to monitoring of the pregnancy.

Women who have a positive pregnancy test during the study will be withdrawn from the study treatment and the procedures for withdrawal will be completed. The Medical Monitor must be contacted immediately to break the blind (if applicable).

All pregnancies, subject or partner of a subject, that occur during the study or come to the attention of the Investigator within 30 days after the last study visit (including the Follow-up Visit) or until 30 days after last study treatment administration, whichever is longer, must be reported to [REDACTED] by the reporting procedures described above.

The outcome of all such pregnancies (including normal births) should be followed up and documented, even if the subject was withdrawn from the study. Every effort should be made to gather information regarding the pregnancy outcome until 90 days (or otherwise as appropriate) post-partum. It will be the responsibility of Aurinia, together with the appropriate support of the Investigator, to obtain this information.

Complications of pregnancy such as abortion (spontaneous or induced), premature birth, or congenital abnormality are considered SAEs and should be reported following the reporting procedures as outlined in Section 10.3.2, [Serious Adverse Events](#). In the event that the site experiences a temporary disruption of the EDC system, a back-up paper Pregnancy Reporting Form will be available for site staff to complete.

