### 4.2 Duration of Subject Participation and Study

The expected duration of subject participation is approximately 25 months. An assessment of vital status will occur at 6 and 12 months post study. The treatment duration is 24 months with a further follow-up visit 4 weeks after last dose (completion or early termination).

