#### **5.4 Adequate/Effective Contraception**

Women of childbearing potential must have a negative urine pregnancy test at Month 12. Two effective forms of contraception must be used simultaneously unless abstinence is the chosen method. Effective contraception must be used before beginning study treatment, during study dosing, and for 6 weeks following discontinuation of study treatment or MMF dosing, even when there has been a history of infertility, unless due to surgical sterilization. Women not of childbearing potential are defined as women without menses for at least 12 consecutive months or surgically sterilized.

Sexually active men, both reproductively competent and vasectomized, are required to use condoms during treatment and for at least 90 days after cessation of study treatment or MMF. In addition, female partners of male subjects are recommended to use an effective contraception during their partner's treatment and for at least 90 days after the last dose of study treatment or MMF. Male subjects are to refrain from making sperm donations during treatment and for at least 90 days after cessation of study treatment or MMF.

An effective and medically acceptable method of birth control means the chance of pregnancy, when using that type of birth control, is less than 1% per year if used correctly. These birth control methods (i.e., reliable forms of contraception) include birth control pills (combined oral contraceptives), hormone implants, hormone shots, and some intrauterine contraceptive devices. The use of MMF in this study can also reduce the effectiveness of the oral contraceptive pill.

Barrier methods (e.g., condoms, diaphragm, or cervical cap/sponge) when used alone are not considered highly effective.

Although abstinence, when adhered to, is an effective method of birth control, other additional effective contraception methods should be used where there is any doubt. The method of contraception needs to be discussed with the Investigator throughout the study period in order to confirm the method used is considered effective.

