### 9.2.4 Follow-up Procedures

All subjects will have a safety follow-up visit after the last dose of study drug at Month 37 ( $\pm 10$  days), to collect any new AEs and concomitant medications. This visit (Visit 24) will be

conducted as an in-clinic visit. An assessment of vital status will also be conducted at 6 and 12 months post study.

Assessments for the follow-up visit are as follows:

- Vital signs (BP, pulse, temperature)
- Blood sample collection for analysis at central laboratory (eGFR)
- FMV urine sample collection
- Concomitant medication
- AEs
- Confirmation of completed follow-up visit using IRT
- Assessment of vital status will occur at 6 and 12 months post study

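### Mandatory pregnancy reporting closes about 58–60 days after last dose for subjects who attend Visit 24, short of the 90-day contraception period for men

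*Protocol*

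**What the plan says.** Protocol Section 5.4 sets two post-treatment contraception periods. Women continue "for 6 weeks following discontinuation of study treatment or MMF dosing". Sexually active men are "required to use condoms during treatment and for at least 90 days after cessation of study treatment or MMF", and their female partners are recommended to use contraception for the same 90 days.

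Protocol Section 10.3.3 has two sentences on what to report. The opening one says that a pregnancy in a subject or a subject's partner *should* be reported within 24 hours of awareness, and gives no end date. A later one says which pregnancies *must* be reported: those that occur during the study, or that come to the Investigator's attention "within 30 days after the last study visit (including the Follow-up Visit) or until 30 days after last study treatment administration, whichever is longer". Outcome follow-up, with every effort to reach 90 days post-partum, is then attached to the pregnancies so defined.

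The last study visit is Visit 24, a "safety follow-up visit after the last dose of study drug at Month 37", with a window of ±10 days. Section 4.2 places it 4 weeks after last dose. The last scheduled pregnancy test is the serum test at Month 36 (Schedule of Events; Section 9.1.1, Table 1). None is scheduled at Visit 24.

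**The concern.** The two sections use different clocks, and nothing in the protocol links them. Section 5.4 treats conception as something to prevent for 90 days (men) or 6 weeks (women) after study treatment or MMF. The obligatory part of Section 10.3.3 counts 30 days from the last visit or from the last study treatment, and MMF does not enter it. For a pregnancy that begins after the study, the test is when the Investigator hears of it, not when conception occurred.

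A site that follows the obligatory sentence literally could therefore leave unreported a pregnancy conceived while the protocol still required contraception. Its outcome would then not be followed. MMF is background therapy for all subjects, and Section 7.2.2.3 requires that subjects be reminded of the pregnancy risk while taking it. Few such pregnancies are likely, so each missing outcome is a real loss of information.

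**Working it through.** The protocol gives no total length for the reporting window, so there is no stated figure to reproduce. The check is day arithmetic with last dose as day 0.

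Inputs:
- Visit 24 at 4 weeks = 28 days (Section 4.2), or one calendar month = 365.25/12 = 30.4 days (Month 36 to Month 37, Section 9.2.4).
- Visit window ±10 days (Schedule of Events).
- Reporting limit of 30 days after the last visit or last study treatment, whichever is longer (Section 10.3.3).
- Contraception for 90 days in men and 6 × 7 = 42 days in women (Section 5.4).

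Formulas: closing day = day of last visit + 30, or 30 if no visit follows last dose. Gap = contraception period − closing day. A negative gap means that the window outlasts the contraception period.

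| Last visit | Day | Closing day | Gap, men (90 − closing) | Gap, women (42 − closing) |
|---|---|---|---|---|
| 4 weeks − 10 days | 18 | 48 | 42 | −6 |
| 4 weeks | 28 | 58 | 32 | −16 |
| 4 weeks + 10 days | 38 | 68 | 22 | −26 |
| 1 month − 10 days | 20.4 | 50.4 | 39.6 | −8.4 |
| 1 month | 30.4 | 60.4 | 29.6 | −18.4 |
| 1 month + 10 days | 40.4 | 70.4 | 19.6 | −28.4 |
| No visit after last dose | – | 30 | 60 | 12 |

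For men who complete treatment and attend Visit 24, a gap of about 20–42 days exists at every permitted visit date. For women who attend Visit 24, the window outlasts the 42 days by 6–28 days.

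Recognition lag adds to this. The documents give no figure, so assume 2 to 6 weeks from conception to the Investigator's awareness. Read *during the study* as up to Visit 24, so that conceptions before that visit have no cut-off. At a 2-week lag, conceptions more than 30 − 14 = 16 days after Visit 24 surface too late. At a 6-week lag, 42 exceeds 30, so every conception after Visit 24 does. A conception on day 42, the end of the women's period, would surface between day 42 + 14 = 56 and day 42 + 42 = 84, against a closing day of 58–60.

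**The case against.** The strongest reply is that Section 10.3.3 opens with a reporting request that has no end date. A reader might infer from the 30-day clause that later pregnancies may go unreported; the documents do not support that, because the opening sentence does not bar later reporting. What remains is an undated *should* beside a time-limited *must*, with outcome follow-up attached to the latter. The two sentences conflict, and a site can satisfy the narrower one.

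Three other stronger readings are tempting.

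- *Women generally have a gap.* They do not if Visit 24 takes place; only late recognition is then at issue.
- *Anyone who stops early is covered for only 30 days.* Sections 5.6 and 9.2.3 ask subjects who stop to continue or complete visits, and the longer limb of the clause then applies, so cover can run many months past last dose. The 30-day case needs no visit at all after last dose. It remains possible, because Section 5.5 makes Visit 24 after withdrawal advisory. Such subjects are also hard to reach under any rule.
- *The primary safety analysis is compromised.* The AE reporting period ends at Visit 24 (Section 10.3.1), and later safety information goes to the safety database only (Section 10.3.2). These pregnancies would not enter the planned AE tables even under a longer rule.

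It is also fair to say that Section 5.4 does not call its periods a reporting window, and that the 30-day limit matches the one for deaths. Section 10.3.2 further requires treatment-related SAEs found after the study to be reported at any time. That captures complications judged related to study treatment, but not the pregnancy itself.

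**Conclusion.** The mismatch is real but narrow. For partners of male subjects who attend Visit 24 after completing treatment, the last 20–42 days of the 90-day period lie outside obligatory reporting, before any recognition lag. For women who attend Visit 24 the calendar periods agree. When no visit follows last dose, 60 of 90 days (men) and 12 of 42 days (women) are uncovered.

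The result assumes that Visit 24 falls 28 to 30.4 days after last dose, ±10 days, and that MMF stops with study treatment. If MMF continues longer, the mismatch grows, because only Section 5.4 counts from MMF. The documents do not allow an estimate of how many of the 216 subjects (SAP Section 6.1.1) or how many pregnancies are affected. The consequence is incomplete pregnancy safety reporting and outcome follow-up. The primary endpoint is untouched. The wording should be corrected because the change is cheap.

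**What to change.** Reconcile Section 10.3.3 with Section 5.4 in one sentence. Require reporting and outcome follow-up of every pregnancy in a subject or partner with estimated conception up to the end of the contraception period in Section 5.4, counted from the later of last study treatment or last protocol MMF, whenever the Investigator becomes aware of it. Align the opening sentence of 10.3.3 with this so that one rule remains. Leave the contraception durations as they are.

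Lengthening the 30 days alone is a weaker remedy. To reach day 90 from a Visit 24 on day 28 it would need 90 − 28 = 62 days (52–72 with the visit window), and an awareness limit would still miss late-recognised pregnancies.

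Optionally, add a pregnancy question to the 6-month assessment. Section 9.2.4 states "An assessment of vital status will also be conducted at 6 and 12 months post study", but does not say that this involves contact with the subject, so the addition applies only where it does. The cost is the amended sentence and a few more pregnancy reports to follow; monitoring a partner's pregnancy still needs her consent, as Section 10.3.3 already provides.

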## **11. CLINICAL ENDPOINTS COMMITTEE**

A CEC will be constituted to adjudicate the following secondary endpoints for subjects in this study:

- Renal flare
- Extra-renal flare

The CEC will adjudicate the endpoints by reviewing blinded data. Aurinia will establish a charter document explaining the working procedures and responsibilities of the CEC. All adjudication decisions of the CEC will be appropriately documented.

## **12. DATA AND SAFETY MONITORING BOARD PROCEDURES**

A DSMB will be constituted to protect the safety of study participants. The DSMB will receive blinded eCRF data in the form of tables and listings (prepared by an independent statistician), and review subject status changes and dosing decisions (where appropriate). Where appropriate, the DSMB may receive unblinded data (on a subject level or treatment group level) that should be reviewed in a closed session. Examples of the data that may be included are: disposition, demographics, baseline characteristics, AE data, SAE data (by severity and causality), laboratory data, dose adjustments, protocol adherence, and subject withdrawals. The DSMB will evaluate the progress of the study, assess data quality and timeliness, participant recruitment, accrual and retention, and participant benefit versus risk. In addition, the DSMB will monitor external factors relevant to the study, for example scientific and therapeutic developments that may affect participant safety or ethical status. Based on the observed benefits or adverse effects, the DSMB will make recommendations to Aurinia concerning continuation, termination, or modifications of the study.

Aurinia will establish a charter document explaining the working procedures and responsibilities of the DSMB. All deliberations and decisions of the DSMB will be appropriately documented.

## **13. STATISTICAL ANALYSIS**

### **13.1 Statistical Methods**

Complete details of the statistical and analytical methods will be provided in a formal Statistical Analysis Plan (SAP), which will be finalized prior to the database lock. A general description of the planned methods is provided below. Any deviation from the SAP will be noted and explained in the clinical study report.

